#### **Growth Status**

Height, bone age, skeletal maturity and epiphyseal status will be analysed for growing children (paediatric).

Linear height velocity, linear height z-scores, knee height velocity, and chronological age will be derived for growing children. Annualised height velocity will be derived once two consecutive measurements are spaced by a minimum of 6 months and a maximum of 12 months.

Actual values and changes from the Baseline Visit in linear height and knee height velocity and the difference between chronological age and bone age will be presented at each visit. Linear height z-scores and change from Baseline until final adult height (defined clinically as last height velocity <1cm/year or radiologically as closed epiphysis of hand-wrist or knee) is achieved will be presented at each visit. The frequency, severity and descriptive details of PPC in growing children will also be presented overall.

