Participants <18 years with open epiphyses were assessed for growth during the clinical studies. PPC was identified in 27 of 102 participants (26%) <18 years of age and was more common in younger (<8/10 years: 14 of 25 participants, 56%) compared with older (≥8/10 to <14 years: 13 of 39 participants, 33%; and ≥14 to <18 years: 0 of 38 participants, 0%) participants. In participants who received only chronic dosing, PPC, when observed, typically occurred between 12 and 18 months. The higher proportion of younger participants with PPC is not unexpected given that pre-adolescent individuals are not expected to have physiologic growth plate closure. Thus, any narrowing, partial closure, or closure are likely to be assessed as premature by the clinician. However, the possibility that younger participants are predisposed to developing PPC or are more sensitive to the effects of palovarotene cannot be excluded.

Palovarotene treatment is currently indicated for children aged 8 years and above for females and 10 years and above for males (or as per the approved indication in locally approved label). However, children between the ages of 4 years and 8/10 years were included in the clinical studies and exposed to palovarotene. The safety profile for palovarotene in participants with

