**PAGE 30 OF 287** 

#### 7.3.1 Safety Profile of Palovarotene

Safety data from the FOP clinical studies reflect exposure to palovarotene in a total of 164 participants, including 139 participants aged 8 years and above for females and 10 years and above for males ( $\geq 8/10$  years; the target population for the FOPal registry study) for a mean duration of 94.1 weeks, to a maximum of 3.8 years. Participants received either:

- Chronic/flare-up regimen 5 mg daily dose of palovarotene with a 20/10 mg dose for 12 weeks at the time of flare-up (4 weeks of 20 mg once daily followed by 10 mg once daily for 8 weeks);
- Flare-up regimen of either the 20/10 mg dose for 12 weeks, a 10/5 mg dose for 6 weeks (10 mg once daily for 2 weeks followed by 5 mg once daily for 4 weeks) or a 5/2.5 mg dose for 6 weeks (5 mg once daily for 2 weeks followed by 2.5 mg once daily for 4 weeks).

In palovarotene-exposed participants aged  $\geq 8/10$  years, the most commonly reported adverse reactions were in the *Skin and subcutaneous disorders* (97.8%), *Gastrointestinal disorders* (75.5%) and *Infections and infestations* (48.9%) System Organ Classes (SOC).

Participants <18 years with open epiphyses were assessed for growth during the clinical studies. PPC was identified in 27 of 102 participants (26%) <18 years of age and was more common in younger (<8/10 years: 14 of 25 participants, 56%) compared with older ( $\geq$ 8/10 to <14 years: 13 of 39 participants, 33%; and  $\geq$ 14 to <18 years: 0 of 38 participants, 0%) participants. In participants who received only chronic dosing, PPC, when observed, typically occurred between 12 and 18 months. The higher proportion of younger participants with PPC is not unexpected given that pre-adolescent individuals are not expected to have physiological growth plate closure. Thus, any narrowing, partial closure, or closure are likely to be assessed as premature by the clinician. However, the possibility that younger participants are predisposed to developing PPC or are more sensitive to the effects of palovarotene cannot be excluded.

Palovarotene treatment is currently indicated for children aged 8 years and above for females and 10 years and above for males (or as per the approved indication in locally approved label). However, children between the ages of 4 years and 8/10 years were included in the clinical studies and exposed to palovarotene. The safety profile for palovarotene in participants with

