- Birth and developmental outcomes through the infant(s)' first year of life.

For growing children with FOP exposed and unexposed to palovarotene:

- Raw values and change from Baseline in linear height and knee height velocity at each Follow-up Visit until skeletal maturity or final adult height is reached;
- Baseline linear height z-scores and change from Baseline at each Follow-up Visit until skeletal maturity or final adult height is reached;
- Mean difference between chronological age and bone age at each Follow-up Visit;
- Frequency, severity and descriptive details of PPC overall and at each Follow-up Visit.

For participants with FOP exposed to palovarotene:

- Mean dose/year for chronic treatment;
- Mean dose/cycle for flare-up treatment.

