#### **Growth Status**

The FOPal registry study will collect bone age, knee height and epiphyseal status ("open/partially closed/closed/not assessable") for growing children at the Baseline Visit, at the first marketed palovarotene intake (for exposed non-naïve participants) and at the Follow-up/End of Study Visits if available.

Growing children are those in whom the growth plates have not fused. Whether the participant is a growing child is based on the investigator's assessment.

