# Comparison of key safety outcomes between the Safety Exposed and the Safety Unexposed Populations

The key secondary endpoints that will be descriptively compared between exposed and unexposed participants with FOP in the FOPal registry, include: 1) Annualised frequency of flare-ups categorised by overall occurrence; 2) Annualised linear height velocity and height z-scores until skeletal maturity or final adult height is reached; knee height may also be evaluated depending on data availability, and 3) Annualised frequency and descriptive characteristics of bone fractures, categorised by overall occurrence and location.

The index date (Day 1) corresponds to the initial administration of marketed palovarotene for the exposed participants (naïve and non-naïve), and to the ICF signed date for unexposed participants.

Participants in the Safety Unexposed Population will be followed from their index date until data extraction at the end of FOPal registry, or until start date of palovarotene, or any investigational or commercialised FOP first treatment intake, whichever comes first.

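### Height z-score and velocity analyses stop at epiphyseal closure of any cause, so height lost after premature closure drops out of the exposed-versus-unexposed comparison

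*Protocol*

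**What the plan says.** Section 9.7.3.4 (Growth Status) presents linear height z-scores and their change from Baseline "until final adult height (defined clinically as last height velocity <1cm/year or radiologically as closed epiphysis of hand-wrist or knee) is achieved". Closure at one of the two sites is enough.

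The velocity endpoint in section 9.3.1.2 has a matching end: "Raw values and change from Baseline in linear height and knee height velocity at each Follow-up Visit until skeletal maturity or final adult height is" (the quote breaks off one word before the end of the sentence). The comparison of key safety outcomes in 9.7.3.4, which uses propensity-score weighting, lists as one of its three outcomes "Annualised linear height velocity and height z-scores until skeletal maturity or final adult height is reached".

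Section 9.3.2.7 says "Growing children are those in whom the growth plates have not fused", and leaves it to the investigator to decide who counts as one.

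Section 7.3.1 explains that in pre-adolescents "any narrowing, partial closure, or closure are likely to be assessed as premature by the clinician". It reports that "PPC was identified in 27 of 102 participants (26%) <18 years of age", with 13 of 39 at ages ≥8/10 to <14 years and 0 of 38 at ≥14 to <18 years.

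None of these sections separates physiological from premature closure when it sets the end of the height analyses.

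**The concern.** The event that ends follow-up of z-score and velocity is one that PPC can produce. Once PPC has gone to complete closure at the knee or hand-wrist, the child meets the radiological definition of final adult height at whatever age that happens. The years in which the child falls behind peers are the consequence of interest, and they come after the stop. The clinical limb has a related fault: it ends the series on a low value of the outcome being analysed.

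Such stops should be commoner in the exposed cohort, because PPC is a recognised effect of treatment in children. The truncation is then informative and differs between the cohorts, and it works towards similar growth in both. Growth is one of only three outcomes chosen for comparison, so a finding of little difference could be read as reassurance that the analysis cannot give.

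**Working it through.** **1. The protocol's own figures.** The strata add up: 14 + 13 + 0 = 27 and 25 + 39 + 38 = 102. The proportions reproduce: 27/102 = 26.5%, 14/25 = 56.0%, 13/39 = 33.3%, 0/38 = 0%. The registry enrols girls from 8 and boys from 10 years up to 18, so the rate across eligible paediatric ages is 13/(39 + 38) = 13/77 = 16.9%. The 33.3% is the highest eligible stratum.

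**2. Children who could meet the stop through PPC.** Sections 9.5 and 9.7.2 plan at least 67 exposed participants, about half of them paediatric: 67/2 = 33.5.

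- At 16.9%: 33.5 × 13/77 = 5.7
- At 33.3%: 33.5 × 13/39 = 11.2

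This is about 6 to 11 children if every PPC goes to complete closure. The documents do not give the share that does.

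**3. Mean velocity hidden by an immediate stop.** Let r be the PPC rate, v the velocity of unaffected children and a the velocity of affected children after closure. The protocol gives neither velocity. I assume v = 4-6 cm/year and a = 0-1 cm/year. Without the stop, the mean is (1 − r)v + ra. With an immediate stop it is v. The hidden amount is r(v − a), in cm/year:

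| r | v − a = 3 | v − a = 4.5 | v − a = 6 |
|---|---|---|---|
| 16.9% | 0.51 | 0.76 | 1.01 |
| 33.3% | 1.00 | 1.50 | 2.00 |

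This compares means over time after closure. Averaged over all follow-up the amount is smaller, because section 7.3.1 places PPC under chronic-only dosing typically at 12 to 18 months.

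**4. Height z-score with a delayed stop.** Suppose growth ceases at closure, peers grow v cm/year, and the SD of height at a given age is s. The child is followed for F years after closure, and the stop takes effect L years after closure. The full loss is vF/s and the loss kept in the analysis is vL/s, so the share kept is L/F. All four inputs are assumptions.

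With v = 5 and s = 6:

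- Full loss per affected child: 5 × 2/6 = 1.67 at F = 2 and 5 × 4/6 = 3.33 at F = 4.
- Loss kept: 0 at L = 0, 0.42 at L = 0.5 and 0.83 at L = 1.
- Shift in the exposed mean without the stop: 0.169 × 1.67 = 0.28 up to 0.333 × 3.33 = 1.11.
- Shift in the exposed mean with the stop: 0 to 0.333 × 0.83 = 0.28.

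For F = 2 or 4 and L = 0 to 1, the share kept runs from 0% to 50%, whatever v and s are.

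**The case against.** A reader might infer that the plan is blind to PPC, or that it records none of the growth loss. The documents do not support either reading.

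- PPC is an endpoint of its own in both cohorts (9.3.1.2), an adverse event of special interest (9.3.2.5) and always reported as serious (11.1.2), so it also reaches the primary safety tables. In unexposed participants it is a medical event of special interest (9.3.2.6).
- Raw linear height is tabulated at every visit for both cohorts with no stop (9.7.3.5, Linear Height and Weight).
- Data up to the stop are kept. Velocity is derived over intervals of 6 to 12 months, so the interval that spans closure already holds part of the slowing.
- Only a closed epiphysis triggers the radiological limb. Section 9.3.2.7 codes partial closure separately. That PPC drives velocity below 1 cm/year is an inference, not a statement of the protocol.
- Fusion at one site does not automatically remove a child from the growing group, since that status is the investigator's judgement.

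All of this stands, and it narrows the point without removing it. PPC is not among the three outcomes compared in 9.7.3.4. Raw height is neither age-standardised nor weighted. The growth measures named for the weighted comparison are the truncated ones. Ending growth summaries at final height is a sensible default for physiological maturity. The gap is that premature closure is treated in the same way.

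**Conclusion.** The point holds for the z-score and velocity analyses and the weighted comparison built on them. As written, PPC that reaches complete closure ends a child's contribution, the later deficit is lost, and the bias runs towards no growth effect.

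The size is illustrative. About 6 to 11 of some 33 exposed children would be affected if all PPC went to closure at the earlier rates. An immediate stop would hide about 0.5-1.0 cm/year of mean velocity after closure at 16.9%, and 1.0-2.0 at 33.3%. Partial PPC or a lag before the stop reduces this. It carries over in full to the difference between cohorts only if PPC is absent in the unexposed, for whom the protocol gives no rate. A reader might take 1.5 cm/year as the expected bias, but that figure applies the rate of the worst eligible stratum to every child and allows no lag.

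This should be fixed, but the study does not fail on it. The comparison is secondary and descriptive, no hypothesis is tested, and the primary objective is unaffected.

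**What to change.** In section 9.7.3.4, and in the matching endpoints in 9.3.1.2:

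1. State that closure recorded as PPC, or velocity below 1 cm/year before physiological maturity, does not end the linear height z-score and velocity analyses.
2. Keep every child who was growing at index in these analyses to a fixed age or the last available height.
3. Present the truncated analysis as secondary, and split the tables by age and sex.

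For linear height this needs no new data, because section 9.3.2.4 already collects it for all participants at clinic visits. There are three costs:

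- Some mature adolescents will contribute near-zero velocities in both cohorts, which is the reason for the split by age and sex.
- Knee height is collected only in growing children (9.3.2.7), so values after fusion would need a change in collection. Knee height can be left out of this change.
- Heights after palovarotene is discontinued will be limited by the withdrawal and follow-up provisions in 9.2.8 and 9.2.9. Some of the later deficit will stay unobserved under any analysis rule, and section 9.9 should say so.

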**PAGE 31 OF 287** 

FOP was consistent across adult ( $\geq$ 18 years) and paediatric ( $\geq$ 8/10 to <18 years) age subgroups except for epiphyses premature fusion. Some mucocutaneous effects such as decubitus ulcers had a higher incidence in adult participants, which was consistent with disease burden, increasing disability and prolonged exposure to corticosteroids.

Radiological vertebral fractures (PT: Spinal fracture) were identified as a risk associated with palovarotene based on retrospective analyses performed on WBCT data in participants with FOP in the Phase 3 (MOVE) study.

No pregnancies were reported during the clinical development programme.

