**PAGE 36 OF 287** 

As this is a non-interventional, observational registry study designed to collect and assess real-world data, exposed participants will receive palovarotene as prescribed by their treating physician, as per local label. Palovarotene will be supplied to the participant according to usual practice, not by the sponsor.

In addition, participants will be treated in accordance with usual medical practice during their participation in the FOPal registry study. No additional assessments or tests will be required by this protocol. All relevant data collected as part of routine medical care will be captured using the electronic Case Report Form (eCRF) by the investigator (patient-reported questionnaires will be completed directly by the participant on paper and returned to the site for data entry into the eCRF) and transmitted to the sponsor. If some assessments are not routinely performed by the investigator, they will not complete the corresponding sections in the eCRF.

The FOPal registry study will collect data at Baseline and at each Follow-up Visit. Follow-up Visits are scheduled as per routine clinical practice (recommended every 6 months).

The duration of the FOPal registry study is up to 11 years, with an enrolment period of maximum 10 years from first participant, first visit, and a minimum of 1 year of data collected for participants who are enrolled within that period.

The primary objective of the FOPal registry study is to collect and assess real-world safety data in participants with FOP exposed to palovarotene, to permit the description and incidence of all treatment-emergent adverse events (TEAEs), serious TEAEs and nonserious TEAEs, whether or not they are considered related to palovarotene and all serious and nonserious treatment-related TEAEs.

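### Final adult height can be declared from one unconfirmed height velocity below 1 cm/year, as little as a 0.5 cm gain over 6 months, and this truncates the velocity and z-score outcomes and the growth comparison

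*Protocol*

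**What the plan says.** Section 9.7.3.4 (Growth Status) gives final adult height two alternative routes: "defined clinically as last height velocity <1cm/year or radiologically as closed epiphysis of hand-wrist or knee". The same section sets how a velocity is obtained: "Annualised height velocity will be derived once two consecutive measurements are spaced by a minimum of 6 months and a maximum of 12 months". No second measurement, minimum age, bone age or check of epiphyseal status is attached to the velocity route.

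On visit timing, Section 9.1 states: "Follow-up Visits are scheduled as per routine clinical practice (recommended every 6 months". The shortest permitted interval for a velocity is therefore also the recommended visit spacing.

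The definition acts as a stopping point. Section 9.3.1.2 reports "linear height and knee height velocity at each Follow-up Visit until skeletal maturity or final adult height is reached", and z-scores carry the same limit. One of the three key exposed-versus-unexposed comparisons in Section 9.7.3.4 is "Annualised linear height velocity and height z-scores until skeletal maturity or final adult height is reached".

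Other growth outputs do not carry this limit. On premature physeal closure (PPC), Section 9.7.3.4 says: "The frequency, severity and descriptive details of PPC in growing children will also be presented overall". The difference between chronological and bone age is not written as ending at final adult height. Section 9.7.3.5 presents raw linear height at every visit with no such stop.

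Section 9.3.2.7 defines the children concerned differently: "Growing children are those in whom the growth plates have not fused", as judged by the investigator. Velocity plays no part in that definition.

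**The concern.** Because the routes are joined by *or*, one low velocity suffices. A child whose growth plates are recorded as open can be a growing child under Section 9.3.2.7 and at final adult height under Section 9.7.3.4. The two definitions conflict whatever the measurement error is.

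The second problem is noise. Heights come from routine care at many sites, in a disease that progressively restricts movement, and Section 9.9 accepts that assessments will vary with local practice. A 0.5 cm difference between two such heights may be mostly error. Vertebral fracture could also lower measured height; Section 7.3.1 records: "Radiological vertebral fractures (PT: Spinal fracture) were identified as a risk associated with palovarotene".

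The stop depends on the outcome being measured, and it falls mainly on slow growers, the children a growth-safety analysis most needs to keep. If growth is slower in one cohort, that cohort loses more child-time. Propensity weighting on baseline covariates does not correct this.

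**Working it through.** **Inputs from the protocol:** cut-off 1 cm/year; interval 6 to 12 months; recommended visits every 6 months. The protocol gives no false-declaration rate to reproduce.

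**Assumed:** SD of a single height measurement, s = 0.3, 0.5 or 1.0 cm; true velocity v constant at 2, 3 or 5 cm/year; independent normal errors.

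**Step 1, the cut-off in centimetres.** 1 cm/year × 6/12 = 0.5 cm at 6 months; 1 × 12/12 = 1.0 cm at 12 months.

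**Step 2, error of a height difference.** The 95% half-width is 1.96 × s × √2, which is 0.83, 1.39 and 2.77 cm for s = 0.3, 0.5 and 1.0. It reaches 0.5 cm at s = 0.5/(1.96 × 1.414) = 0.18 cm. So 0.5 cm lies inside the error of the difference for any s above about 0.18 cm.

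**Step 3, one pair of heights.** P(observed velocity < 1) = Φ((1 − v) × t/(s√2)), with t in years. For v = 3, t = 0.5, s = 0.5: Φ(−1.0/0.707) = Φ(−1.414) = 7.9%.

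| True velocity | One 6-month pair, s = 0.3 / 0.5 / 1.0 | One 12-month pair |
|---|---|---|
| 2 cm/year | 12% / 24% / 36% | 0.9% / 7.9% / 24% |
| 3 cm/year | 0.9% / 7.9% / 24% | 0% / 0.2% / 7.9% |
| 5 cm/year | 0% / 0.2% / 7.9% | 0% / 0% / 0.2% |

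**Step 4, two years of follow-up, with the first low value treated as final.** Successive differences share a height, so this was simulated: four 6-month pairs, or two 12-month pairs. The last column requires two consecutive low 6-month intervals.

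| True velocity | Any 6-month pair, s = 0.3 / 0.5 / 1.0 | Any 12-month pair | Two consecutive 6-month pairs |
|---|---|---|---|
| 2 cm/year | 43% / 75% / 93% | 2% / 16% / 46% | 0.4% / 5% / 17% |
| 3 cm/year | 4% / 29% / 75% | 0% / 0.5% / 16% | 0% / 0.1% / 5% |
| 5 cm/year | 0% / 0.9% / 29% | 0% / 0% / 0.5% | 0% / 0% / 0.1% |

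**Step 5, direction of the distortion.** Two cohorts were simulated with true velocities drawn from normal distributions with means 3 and 5 cm/year and SD 1.5. Only children truly growing at least 1 cm/year were kept, so every declaration is false. The true difference is 1.75 cm/year. Four 6-monthly pairs were taken, and the low value that triggers the stop was included.

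- By-visit difference at the fourth pair: 1.55, 1.52 and 1.73 for s = 0.3, 0.5 and 1.0. It is attenuated at 0.3 and 0.5 and hardly changed at 1.0.
- Difference in per-child mean velocity: 1.82, 1.94 and 2.10. It is exaggerated, because the triggering low value counts and the rebound after it is lost.
- With two-interval confirmation: by-visit 1.73, 1.72 and 1.74; per-child 1.75, 1.76 and 1.80.

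**The case against.** The strongest reply is that the 6-monthly figures describe the worst permitted spacing. Section 9.4 says formal in-person visits may be annual, and the footnotes to Tables 2 to 4 do not expect height at telephone or video visits. With annual heights the risk falls sharply (Step 4). This stands, and both spacings belong in any statement of size.

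Second, *last* height velocity could mean the most recent value at analysis, so that a later, higher velocity would supersede a low one. The single-pair figures in Step 3 would then apply. The text does not settle this. On that reading the definition still rests on one unconfirmed pair, and it is hard to operate as a limit applied at each visit.

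Third, the measurement SD is assumed. A reader might take it as established that 0.5 cm is within measurement error. The documents give no error figure, so this holds only under the stated range.

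Fourth, a reader might infer that growth follow-up ends or that children leave the growth analysis altogether. The documents do not support that: heights continue to be collected, and only the velocity and z-score outputs and the comparison built on them are truncated.

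Finally, the study is descriptive and leaves technical detail to the SAP. No test or sample size is affected. But the protocol itself fixes this definition, and it reports comparative estimates with 95% confidence intervals, which outcome-dependent truncation can bias.

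**Conclusion.** The point holds for the height-velocity and z-score outcomes and the cohort comparison that uses them. The conflict with Section 9.3.2.7 and the absence of confirmation are plain from the text and need no assumption. The size does: it depends on the measurement SD, the spacing of heights, and whether the first low value is final. For a child growing 3 cm/year over two years it ranges from about 0% (annual heights, SD 0.3 cm) to 75% (6-monthly, SD 1.0 cm); at 2 cm/year, from 2% to 93%. Faster growers are largely unaffected unless the SD is near 1 cm.

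A reader might infer that the bias always runs toward no harm. That is not supported. In Step 5, by-visit differences were attenuated at later visits for SDs of 0.3 and 0.5 cm, while differences in per-child means were exaggerated. The defensible conclusion is that the comparison is distorted in a direction that depends on the summary chosen.

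**What to change.** In Section 9.7.3.4, for the purpose of the analysis, treat final adult height as reached only when one of these is met:

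- velocity below 1 cm/year in two consecutive intervals, where heights are about 6 months apart and the two intervals together span at least 12 months;
- velocity below 1 cm/year over one interval of about 12 months, with no epiphysis recorded as open;
- the epiphysis of the hand-wrist or knee recorded as closed.

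Keep all heights in the velocity and z-score analyses until then. Reconcile this with the definition of growing children in Section 9.3.2.7, so that it is clear which governs when plates are open and velocity is low.

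The cost is a short change to one definition, with no new data. With 6-monthly heights, a true end of growth is recognised about 6 months later. Some false declarations remain for very slow growers with noisy heights (17% at 2 cm/year and SD 1.0 cm). With annual heights, the protection comes from recorded epiphyseal status, so it is weaker where that status is missing.

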# 9.2.4 Registry Study Duration

The duration of the FOPal registry study is up to 11 years, with an enrolment period of maximum 10 years from first participant, first visit, and a minimum of 1 year of data collected for participants who are enrolled within that period.

Participant enrolment will start on the date that palovarotene is commercially available in any given country for exposed participants, and once the investigational site has been activated for all participants.

The investigator must ensure that the participant receives appropriate medical follow-up and this should be properly documented in the participant's medical records and eCRFs regarding:

- AEs or their sequelae (any AE, based on the investigator's opinion, not only those assessed as related) that persist after the date of palovarotene discontinuation for exposed participants.
- Medical events of special interest (growth outcomes, including PPC, and fractures) for unexposed participants for the entire study duration.

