# 9.2.8 Registry Study Discontinuation/Withdrawal

The participant can withdraw (or be withdrawn if the subject is a child upon legal representative's decision) from the FOPal registry study at any time. The date and primary reason for withdrawal should be recorded in the eCRF as well as whether the participant stopped or not palovarotene for exposed participants.

Should the participant withdraw from the study, no further data will be collected, nevertheless, data collected up to the time of the withdrawal will be kept for analysis, safety and integrity of study results.

The participant will be withdrawn from the FOPal registry study if:

- The participant enrols in any interventional clinical trial for FOP, or,
- For exposed participants: the participant is no longer receiving palovarotene (except if palovarotene is discontinued due to a safety concern or pregnancy, in such cases the participant will be monitored for safety, see Section 11.4 for follow-up of AEs and Section 11.1.3.1 for follow-up of pregnancies).
- For unexposed participants: the participant becomes pregnant or starts a treatment for FOP other than palovarotene. In case the participant starts palovarotene, they should have the option to remain in the registry. Previously unexposed participants starting palovarotene and remaining in the registry will follow the exposed naïve participants schedule (Table 2) from the first marketed palovarotene intake.

Investigators, participants or/and parents may decide to stop the participation in the FOPal registry study at any time without consequences on the normal participant clinical care.

PAGE 50 OF 287

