#### 9.7.3.1 Statistical Analyses – General Considerations

The statistical analyses will be performed by an external SP, managed by the sponsor's Medical Affairs Biometry Department.

Statistical evaluation will be performed using Statistical Analysis System (SAS)® (Version 9.2 or higher).

No formal statistical testing will be performed and all the analyses will be primarily descriptive in nature. When appropriate and unless otherwise specified, 2-sided 95% CI will be displayed and if p-values are presented, they will be for exploratory purposes only.

Descriptive summary statistics will include the number of documented data, number of missing data and the following:

- Mean, standard deviation, 95% CI of the mean/median when appropriate, median, minimum and maximum for continuous variables;
- Frequency count and percentages for categorical nominal variables.

Missing data will not be replaced but will be summarised in all relevant tables.

Percentages will be based on the number of non-missing observations.

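### Premature physeal closure is summarised as a crude percentage that ignores unequal time at risk, so it will tend to understate the cumulative risk and will not compare fairly between cohorts

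*Protocol*

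**What the plan says.** Section 9.3.1.2 lists PPC as a secondary endpoint for growing children, exposed and unexposed: "Frequency, severity and descriptive details of PPC overall and at each Follow-up Visit". The analysis text in section 9.7.3.4 (Growth Status) says: "The frequency, severity and descriptive details of PPC in growing children will also be presented overall". Section 9.7.3.1 fixes what a frequency is: "Frequency count and percentages for categorical nominal variables", and "Percentages will be based on the number of non-missing observations". No person-time rate, cumulative incidence or other time-to-event summary is stated for PPC. In the same endpoint list, flare-ups and bone fractures are annualised.

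Three other passages determine how long a child is observed.

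- Section 9.2.4: "The duration of the FOPal registry study is up to 11 years, with an enrolment period of maximum 10 years", with "a minimum of 1 year of data collected for participants who are enrolled within that period".
- Section 9.2.8 withdraws an exposed participant if "the participant is no longer receiving palovarotene (except if palovarotene is discontinued due to a safety concern or pregnancy"). Sections 9.2.9 and 9.3.2.5 end follow-up and adverse event collection 30 days after the last intake.
- Section 9.2.4 has unexposed participants followed for growth outcomes, PPC included, over the whole study. Section 9.2.8 withdraws them if they become pregnant or start another FOP treatment.

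On timing, section 7.3.1 reports: "In participants who received only chronic dosing, PPC, when observed, typically occurred between 12 and 18 months".

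**The concern.** PPC is the paediatric harm that the protocol itself singles out. Sections 4 and 7.3.1 describe the safety profile as consistent between adults and children except for premature epiphyseal fusion, and section 11.1.2 requires every PPC to be reported as serious. A percentage with all children in the denominator counts a child who left at month 10 as a full non-event, although on the sponsor's own data the usual onset window had not yet opened. The more children leave early, the lower the percentage, whatever the true risk.

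The by-visit summary does not repair this. A percentage of those still attending a visit is not the probability of having had PPC by that time.

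The two cohorts also lose follow-up for different reasons. Stopping palovarotene ends observation for exposed children only, so a difference between two crude percentages mixes PPC risk with length of observation.

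**Working it through.** **Reproducing the protocol's figures (section 7.3.1).** 27/102 = 26.5%; under 8/10 years 14/25 = 56.0%; 8/10 to under 14 years 13/39 = 33.3%; 14 to under 18 years 0/38 = 0%. The parts add up: 14 + 13 + 0 = 27 and 25 + 39 + 38 = 102. These agree with the printed percentages.

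**Inputs for the size of the bias.**

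- True eventual risk R = 13/39 = 0.333. This is an assumption that borrows the trial figure for ages 8/10 to under 14.
- Onset in cases uniform over t = 1.0 to 1.5 years. The window comes from section 7.3.1; its uniform shape is assumed.
- Administrative follow-up uniform from 1 to 11 years, from section 9.2.4 with even accrual assumed.
- Constant yearly stopping proportion d, independent of PPC. The protocol gives no value, so 0 to 30% is shown. Observation ends 30 days (0.082 years) after stopping, per sections 9.2.8 and 9.2.9.

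**Formula.** An event at time t is seen if administrative follow-up reaches t and the child has not stopped more than 30 days before t:

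share of events seen = average over t in [1.0, 1.5] of [(11 − t)/10] × (1 − d)^(t − 0.082)

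crude percentage = R × share seen

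The share of children with under 18 months of follow-up is 1 − 0.95 × (1 − d)^(1.5 − 0.082).

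| Stopping per year (assumed) | Share with <18 months | Share of events seen | Crude % if true risk is 33.3% |
|---|---|---|---|
| 0% | 5% | 0.975 | 32.5% |
| 10% | 18% | 0.862 | 28.7% |
| 20% | 31% | 0.752 | 25.1% |
| 30% | 43% | 0.644 | 21.5% |

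Simulation of the same scenarios gave 32%, 29%, 25% and 22%. A Kaplan-Meier estimate at 24 months returned the assumed 33% in each. Widening onset to 6 to 24 months left the crude figures almost unchanged. The share of events seen does not depend on R.

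If follow-up were only 1 to 3 years, the factor (11 − t)/10 becomes (3 − t)/2. The crude figure is then 0.333 × 0.875 = 29.2% with no stopping and 0.333 × 0.676 = 22.5% with 20% stopping per year.

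**Age mix.** With trial risks of 33.3% and 0% in the two paediatric bands, a pooled figure is 0.333 × the share aged under 14. That is 8%, 17% or 25% when the share is 25%, 50% or 75%.

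**The case against.** The protocol calls its analysis section a summary and leaves technical detail to a statistical analysis plan that is not shown and could add a time-to-event table. That is fair. The choice between an annualised and a crude measure is nevertheless made in the protocol's endpoint list, and for PPC it is the crude one.

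PPC is not among the outcomes listed for the weighted exposed-unexposed comparison in section 9.7.3.4, so no formal contrast is planned. That stands, but the endpoint is defined for both cohorts and readers will set the two percentages side by side.

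The 12 to 18 month window is stated only for chronic-only dosing. Retrospective data also lengthen observed exposure for some non-naïve participants. Both points make the size less certain but do not reverse the direction.

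Three stronger readings are tempting and are not supported:

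- A reader might infer that the 1-year minimum by itself makes the reported risk badly low. One year is the floor of a 1 to 11 year range. With even accrual and no stopping, only 2.5% of events are lost. Withdrawal on stopping the drug is the larger driver, and its rate is unknown.
- A reader might apply the trials' 94.1-week mean exposure as an exponential dropout time and conclude that 33% would be reported as 17%. This is circular: 33% is already a crude trial frequency, and 94.1 weeks is the mean exposure in those same studies (for all participants aged 8/10 and over, adults included).
- A reader might infer that PPC is reported only as one pooled figure. Section 9.3.1.2 adds each visit, section 9.7.3.2 tabulates adverse events of special interest, and section 9.7.4 plans age subgroups, although without naming bands.

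**Conclusion.** The concern holds in a limited form. As planned, the PPC percentage ignores time at risk. It will tend to fall below cumulative risk, and exposed and unexposed percentages are not comparable when follow-up differs. The shortfall runs from about 1 percentage point with no stopping to about 12 points at 30% stopping per year (33.3% against 32.5% and 21.5%). These figures rest on the assumed true risk, even accrual, 12 to 18 month onset and stopping unrelated to PPC; the documents do not fix the actual size. Cumulative incidence that censors at stopping describes risk under continued treatment, and should be labelled so. This is a worthwhile improvement to a descriptive secondary endpoint. It does not invalidate the registry.

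**What to change.** In sections 9.3.1.2 and 9.7.3.4, keep the crude count and add cumulative incidence of PPC by time since index date, for example at 12, 18 and 24 months, with 95% confidence intervals and numbers at risk, for exposed and unexposed growing children. Section 9.7.3.4 already defines the index date for both cohorts. Censor at the last epiphyseal assessment, end time at risk at skeletal maturity, and use delayed entry for non-naïve participants where PPC data before consent are incomplete. Within the age subgroups already planned in section 9.7.4, split paediatric PPC results at 14 years where numbers allow. None of this changes treatment or withdrawal rules.

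The cost is wording and one table or figure. Event dates, time to onset and epiphyseal status are already collected (sections 9.3.2.5 and 9.3.2.7), as are PPC events in unexposed participants (section 9.3.2.6). The downside is imprecision. Half of 67 and of 33 gives about 33 exposed and 16 unexposed children. Even with complete follow-up, a 33% risk in 33 children has a 95% half-width of about 1.96 × √(0.333 × 0.667/33) = 16 percentage points, and it would be wider in age bands. Epiphyseal assessments follow routine care, so onset times will be known only to within irregular intervals.
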